8.5 Treatment procedures

- Ciprofloxacin: 500 mg, twice daily for 1 week (oral)
- Placebo: one capsule, twice daily for 1 week.

Patients will commence the study medication on the day of screening (visit 1)

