12.1 Outcomes

12.1.1 Primary outcome

The primary outcome will be the time in days to the first day of the next exacerbation following IMP start (at day 0, 14 days after the initial exacerbation), up to a maximum of 90 days. Exacerbation is defined fully below. Patients who do not suffer a recurrent exacerbation will be censored at the end of follow-up / time of drop-out.

The onset of the next (recurrent) exacerbation will be defined as **either**:

- 1) The first day of treatment with antibiotics and/or steroids for an exacerbation of COPD (HCU definition), **or**
- 2) The first of two or more consecutive days of increased respiratory symptoms recorded on the daily diary cards, either:
 - a. Two 'major' symptoms (increased dyspnoea, increased sputum volume, or increased sputum purulence), **or**
 - b. One 'major' and one 'minor' symptom (cold, wheeze/chest tightness, sore throat, cough or fever).

A recurrent exacerbation will only be diagnosed based on diary cards if there are a minimum of five symptom-free days after the end of the previous exacerbation.

The end of the first exacerbation will be defined as the first day of two consecutive symptom-free days.

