The percentage of missing data will be summarised and spurious data double checked as far as possible. Primary analysis will be intention to treat, and so every effort will be made to collect all follow-up data from non-compliers and patients who discontinue treatment. All patients will be analysed from the date of randomisation until end of follow-up period or the date of drop-out. The primary analysis will therefore assume patients who drop-out of the trial do so 'at random'.

Secondary outcome analysis

For each secondary outcome, two analyses will be undertaken – the first adjusting for centre and the baseline value of the endpoint being analysed (where available), and the second also taking into account the additional baseline characteristics specified in the supporting analysis of the primary outcome above.

When modelling continuous data, transformations will be undertaken as necessary to normalise the data. Where appropriate, analyses will take account of length of follow up as an offset, and also account for differences in at-risk periods. Summary measures of the secondary outcomes will be presented (mean, standard deviation, median, interquartile range for continuous variables, percentages for categorical variables) by treatment group and for both baseline and end of trial follow-up visits. The percentage of missing data will be summarised.

Secondary outcomes

- Time until *resolution* of first exacerbation will be compared between the active treatment and placebo groups, using Cox proportional hazards regression, stratified by centre.

• Duration of first exacerbation: dur

- The number of treatment-related adverse events will be analysed by using negative binomial regression. Negative binomial regression models collapse to Poisson regression if there is no overdispersion.

• Number of treatment-related AEs: trt.rltd.aes

- Exacerbation frequency: The rate of exacerbations experienced during the study period per person-year will be analysed by using negative binomial regression.

• Number of exacerbations: excns

- Frequency of antibiotic courses: The rate of antibiotic courses received for patients in the active treatment and placebo groups will be compared using negative binomial regression.

- The rate of hospital attendances during the study period will be analysed by negative binomial regression. .

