In the primary analysis, sensitivity analyses will be undertaken: The efficacy of the IMP will be investigated using a per-protocol analysis. Such an analysis includes only patients who comply fully.. This is in contrast to the main intention to treat analysis, which includes as much patient data as possible, regardless of loss to follow up or ending treatment. If there is great discrepancy between both sets of results, then further investigation will be undertaken using inverse probability-of-censoring weights (IPCW).

Interim analysis

An interim analysis will not be required on the primary end point. The IMP has a wellestablished safety record and is being administered for a short course only; all treatment-related adverse events will be reviewed with the PI and trial steering committee during the trial. If there is suspicion that the IMP is acting outside its normal safety profile then further analysis will be undertaken.

Both the sponsor and the investigator reserve the right to terminate the study at any time. Should this be necessary, the procedure for an early termination or temporary halt will be arranged after consultation by all involved parties. This will be recorded in the CRF and documented in the final report. Unblinding at this point is unlikely to be necessary.

The sponsor will submit a written notification to the Regulatory Authority concerned and Ethics Committee/Institutional Review Board providing the justification of premature ending or of the temporary halt.

Other statistical considerations

Any deviations from the statistical plan will be discouraged. However, any unforeseen changes will be described and justified in the final report, as appropriate. The sponsor, CI, TMG and or DMC will be notified of these deviations. Where required the sponsor and Chief Investigator will notify REC, Regulatory Authorities and the funder.

References

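### The per-protocol set is chosen on compliance seen inside the outcome window, so its hazard ratio can be biased either way, and the IPCW check would probably not be triggered

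*SAP*

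**What the plan says.** The SAP makes ITT primary: "Primary analysis will be intention to treat, and so every effort will be made to collect all follow-up data from non-compliers". Under Sensitivity analysis it adds one alternative: "The efficacy of the IMP will be investigated using a per-protocol analysis". Membership is defined in one sentence, "Such an analysis includes only patients who comply fully", and IPCW is held in reserve: "If there is great discrepancy between both sets of results, then further investigation will be undertaken" by that method. The SAP gives no compliance cut-off, no threshold for the discrepancy and no covariates for the weights. Protocol 12.3 describes ITT only.

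Timing comes from other sections:
- Outcome clock: Protocol 12.1.1 has "The primary outcome will be the time in days to the first day of the next exacerbation following IMP start"; the SAP (Primary outcome analysis) has "All patients will be analysed from the date of randomisation until end of follow-up period or the date of drop-out". Protocol 8.5 starts the capsules on the day of visit 1, which is also when patients are randomised, so both clocks begin at day 0.
- Compliance: the course lasts one week (Protocol 8.5). Capsules are counted at V2, day 7 to 10 (Protocol 8.6; SAP, Study variables and endpoints), and the diary records missed doses during that week (Protocol 9.8.1; SAP, Compliance to the IMP).
- Level: Protocol 9.8.1 sets no minimum compliance with the IMP, and 9.8.2 treats compliance with study procedures separately. The SAP does not say which of the two has to be full.

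**The concern.** Compliance is observed during days 0 to 7, while primary events are already accruing. Selecting on it means selecting on behaviour after randomisation, and possibly on the outcome. There are two routes to bias. A patient whose exacerbation in week 1 interrupts the capsules leaves the per-protocol set and takes the event along. Separately, patients at higher risk may stop more often in one arm than in the other, so those left are no longer comparable.

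The documents make a link between stopping and outcome plausible without stating it. Protocol 10.4 treats an admission for exacerbation as a frequent serious adverse event, and the SAP stops study medication, with follow-up continued, for an adverse event that prevents further participation. The risk table in Protocol 3.4 links dyspnoea, which is also a major exacerbation symptom, to stopping the IMP if causality is suspected. It lists nausea and diarrhoea as common drug effects, which is a reason to stop found mainly on active treatment.

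At stake is the only analysis labelled as one of efficacy. The method meant to check it runs only if someone judges, after seeing results, that two estimates differ greatly.

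**Working it through.** **1. The plan's own figures.** Inputs (SAP, Sample size): N = 138, 5% dropout, control 90-day exacerbation-free survival 0.45. Protocol 12.2.1 gives two-sided 5%.
- n = 138 × 0.95 = 131.1, about 65.5 per arm.
- HR 0.46: active survival 0.45^0.46 = 0.693; events = 131.1 × (0.550 + 0.307)/2 = 56.2. Freedman power = Φ(√56.2 × 0.54/1.46 − 1.96) = 79.2%, against 80% stated.
- HR 0.39: active survival 0.732; events = 131.1 × (0.550 + 0.268)/2 = 53.6; power = Φ(√53.6 × 0.61/1.39 − 1.96) = 89.5%, against 90% stated.

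The design figures reproduce and serve as the base.

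**2. Events inside the compliance window**, assuming a constant hazard:
- Placebo: 1 − 0.45^(7/90) = 6.0%, or 65.5 × 0.060 = 3.9 patients. As a share of placebo events, 0.060/0.55 = 11%.
- Active at HR 0.46: 1 − 0.45^(0.46 × 7/90) = 2.8%, or 65.5 × 0.028 = 1.8 patients.

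These are probably upper figures. Protocol 12.1.1 requires five symptom-free days before a diary-defined recurrence, and many patients enter because symptoms persist, so early events would mostly be treatment-defined.

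**3. Effect on the hazard ratio.** Simulation: exponential times, n = 131, 4,000 trials per scenario, unadjusted Cox model. The stopping rates are assumptions. With a true HR of 1, ITT stayed at 0.99 to 1.01 throughout.

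| Assumed stopping | Per-protocol HR |
|---|---|
| All week-1 exacerbators dropped, both arms | 1.01 (events 72 to 64) |
| 50% dropped on placebo, 100% on active | 0.94 |
| 0% on placebo, 100% on active | 0.89 (type I error 7.4%) |
| 30% of patients at three times the hazard; of these 5% stop on placebo, 40% on active; 5% of the rest stop in both arms | 0.91 (type I error 6.3%) |

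Under the null the arms are interchangeable, so reversing the imbalance gives reciprocals: 1/0.94 = 1.06 and 1/0.89 = 1.12. One intermediate pair of runs gave 0.92 and 1.08. With a true HR of 0.46, dropping all week-1 exacerbators in both arms leaves the HR unchanged but lowers power from about 82% to 77%. Dropping 0% on placebo and 100% on active moves the HR from about 0.46 to 0.41.

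**4. Would the trigger fire?** With 72 events the standard error of the log hazard ratio is about 2/√72 = 0.236. The largest null shift is |ln 0.89| = 0.117, and 0.117/0.236 = 0.49, half of one standard error of the ITT estimate. At HR 0.46 with 56 events: |ln(0.41/0.46)| = 0.115, and 2/√56 = 0.267, a ratio of 0.43. Few readers would call either a great discrepancy. Nor does agreement between the two estimates show that bias is absent.

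**5. Does the alternative rule help?** If compliance is judged only up to the event, the events lost in the first three rows are kept and the estimate returns to the ITT value. In the last row, censoring at the day of stopping does not help by itself: with stopping days spread evenly over the week, a repeat run still gave about 0.9. That part needs weights.

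**The case against.** Much of the opposing case stands.
- No section says that capsules stop when a recurrence is treated. Protocol 8.9 and 9.3 allow treatment for exacerbation as concomitant medication, and neither document's discontinuation list names exacerbation. A patient could exacerbate on day 4, finish the course and count as fully compliant. A reader might infer that week-1 exacerbators are excluded with their events; the documents support only that they can be.
- A reader might infer that the bias runs towards no effect. That needs placebo to lose more of its high-risk patients. The reverse pattern produces a spurious benefit, and equal loss produces almost no bias. Nothing in the documents selects among these.
- The numbers are small: about four placebo and two active patients before asking who stops.
- ITT is primary, non-compliers are followed, the per-protocol analysis is labelled as sensitivity, and the SAP compares adherence between arms, which would reveal unequal non-compliance.
- IPCW is not a guaranteed cure. It works only if the predictors of stopping are measured and modelled. At an assumed 10% non-compliance there would be 0.10 × 138, about 14, non-compliers, which makes for unstable weights.

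These points limit the size of the problem and leave the direction open. They do not supply a definition of full compliance, and they do not remove the data-dependent step.

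**Conclusion.** The concern holds, at the level of a worthwhile improvement. The per-protocol set is selected on compliance observed inside the outcome window, and IPCW waits on an undefined judgement made after results are seen. If stopping is related to outcome or prognosis differently by arm, a true HR of 1 could appear as about 0.9 to 1.1. If it is equal, the cost is events and power. The sizes rest on a constant hazard, on assumed stopping rates and on stopping at week-1 events. A reader might go further and infer that the trial's main efficacy conclusion is biased. The documents do not support that, because the primary analysis keeps every patient in the randomised arm whatever the compliance.

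**What to change.** Amend the SAP's Sensitivity analysis section as follows.
1. Define compliance as compliance with the IMP, from pill count and diary, and state numerically what full means.
2. Judge it only up to the first exacerbation or day 7, whichever comes first. Patients compliant until then stay in, with their event. Others are censored at first non-compliance, dated from the diary, rather than excluded.
3. Report this per-protocol analysis however it compares with ITT.
4. Add IPCW as an unconditional supporting analysis, with a small set of baseline predictors named before unblinding, for example from the covariates of the SAP's additional supporting model. Delete the discrepancy trigger.
5. Keep ITT primary.

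The cost is a few sentences and a little more analysis; pill counts and diary entries are already collected. The weights will be imprecise if non-compliers are few. Baseline predictors will not capture stopping caused by worsening just before an event, so the report should state that limit.
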